1.1 PROTOCOL SUMMARY AND/OR SCHEMA

1.2 Summary

This will be a single-institution, non-randomized, pilot study for 7 patients at MSKCC Main Campus.

We wish to study ribavirin in this patient population because: (1) eIF4E can function as an oncogene; (2) we have recently found that expression of phosphorylated eIF4E is associated with p16-positive tonsillar squamous cell carcinoma (3) ribavirin has been shown to decrease eIF4E levels *in vivo*.

The Primary Aim of this pilot study is to explore if ribavirin therapy for 2 weeks decreases tumor expression of phosphorylated eIF4E among patients with tonsillar and/or base of tongue squamous cell carcinoma.

Subjects will have tonsil and/or base of tongue squamous cell carcinoma that is previously untreated.

Subjects will not have a history of more than 10 pack-years of tobacco use. Subjects will have had a prior diagnostic surgical or core needle biopsy. Patients for whom definitive local-regional treatment (primary surgery or primary radiation therapy +/- chemotherapy, given sequentially or concurrently) is planned will be offered participation in the study. Subjects will take ribavirin 800 mg/day in divided doses for two weeks, which is a standard time frame for pre-operative planning. Patients will be evaluated in clinic by the medical oncologist during week 1 and week 2. (For patients who undergo research biopsy, this will be performed in the clinics of the Head and Neck Disease Management Team.)

Patients will be considered done with treatment at time of surgery and/or research biopsy.

Post-surgical (or post research biopsy) management will be off protocol, according to established standards of care.

1.3 Schema

New Diagnosis Tonsil and/or Base of Tongue SCC

- 10 unstained slides must be available from the initial diagnostic biopsy
- Written Informed Consent

Treatment

- Ribavirin 800 mg/day, in 2 divided doses, for approximately 14 days
- Day 1, Day8: H&P, CBC, comp panel

Approximately Day 15

- Surgery or Research Biopsy at MSKCC
- Discontinue Ribavirin

Off-Study

- Patients are off-study as of Day of Surgery (or Research Biopsy)
- Post-operative (or post Research Biopsy) management is off protocol, per standards of care

2.1 OBJECTIVES AND SCIENTIFIC AIMS

2.2 Primary:

2.1.1

To explore if ribavirin therapy for 2 weeks prior to tumor resection decreases tumor expression of phosphorylated eIF4E among patients with tonsillar and/or base of tongue squamous cell carcinomas that express phosphorylated eIF4E.

2.3 Secondary:

2.2.1

In pre- and post-treatment tumor samples, to explore the pharmacodynamic effects of ribavirin on molecules that may be regulated, directly or indirectly, by eIF4E (eg, p16, p21, EGFR, p53).

2.2.2

In pre- and post-treatment tumor samples, to explore if ribavirin reduces the expression of HPV-16 oncoproteins E6 and E7

3.1 BACKGROUND AND RATIONALE

3.2 HPV/p16-positive HNSCC is a distinct clinical and biological entity

HNSCC comprises at least two distinct clinical entities: HPV-positive tumors and HPV-negative tumors (1). Approximately half of oropharynx (tonsil, base of tongue) squamous cell carcinomas are HPV-positive, but tumors arising at other sites in the upper aerodigestive tract (i.e., oral cavity, hypopharynx, or larynx) generally are not associated with HPV (1). HPV-negative tumors typically occur in individuals with histories of tobacco abuse, whereas HPV-positive HNSCC usually is not associated with tobacco abuse (2, 3). In a prospective randomized clinical trial of cisplatin plus concurrent radiation in HNSCC, HPV-positive squamous cell carcinomas arising in the oropharynx were associated with superior overall survival compared with HPV-negative oropharynx tumors (4).

Potentially, differences in the molecular pathogenesis mechanisms of these tumors account for their distinct treatment responsiveness. Landmark cytogenetic studies of HNSCC demonstrate frequent gene loss at the locus encoding p16 and p14 (CDKN2A), and amplification at the gene locus encoding cyclin D1 (5-7). Whereas p16 loss and cyclin D1 amplification characterize HPV-negative (tobacco-related) tumors, p16 overexpression and downregulation cyclin D1 typify HPV-positive tumors (8). The high p16/low cyclin D1 profile in HPV-positive tumors is due to loss of negative feedback on p16 when the E7 viral oncoprotein inactivates the pRB tumor suppressor protein (1, 9). Immunohistochemical detection of p16 is a marker for HPV-associated carcinogenesis in HNSCC (10-12).

In summary, HPV-positive and HPV-negative head and neck cancers are distinct at the molecular pathology level. There are converse molecular profiles for HPV-positive tumors

(ie, overexpression of p14 and p16; downregulation of cyclin D1; p53 wildtype) and HPV-negative tumors (ie, overexpression of cyclin D1; downregulation p14, p16 and p21; p53 mutant) (3, 8, 10, 13-15), and these molecular profiles can inform the development of clinical studies.

3.3 Rationale for targeting eIF4E in HPV/p16-positive tumors

The translation initiation factor eIF4E is a central regulator of gene expression (16). eIF4E binds the 7-methyl guanosine (m^7G) cap structure in the 5' end of mRNAs, and selectively stimulates the translation of several oncogenic transcripts that are repressed under normal circumstances. Malignancy related mRNAs that are regulated at the level of translation by eIF4E include cyclin D1, VEGF, bcl-2, MMP-9 and Pim-1 (16, 17). Wendel and colleagues demonstrated that eIF4E functions as an oncogene and confers resistance to therapeutic mTOR inhibition in a murine lymphoma model (18, 19).

In 1999 clinicopathologic study of 65 HNSCC surgical cases, Nathan and colleagues reported that expression of eIF4E was detectable by immunohistochemistry in all of the tumors.

Expression of eIF4E in histologically tumor-free margins was present in 55% of specimens, and was associated with a significantly increased risk of tumor recurrence (20).

This group subsequently demonstrated that antisense inhibition of eIF4E mRNA reduced the malignant properties of a HNSCC cell line (FaDu), as measured by increased contact inhibition, reduced growth in soft agar, and reduced tumor growth in xenograft mouse models (21). Growth inhibitory effects also were observed when another HNSCC cell line (UMSCC22B) was subjected to eIF4E silencing with siRNAs (22). As further evidence of eIF4E's central role in translation regulation in HNSCC cells, eIF4E-targeted suicide gene therapy in a murine model of HNSCC (SCC-7 cells) improved disease-free survival (23).

Our current interest in eIF4E in head and neck cancer is an offshoot of our DMT's research program into inhibitors of the PI3K/Akt/mTOR pathway (IRB 06-129, IRB 08-138, IRB 09-028, IRB 09-131). To explore if expression levels of any proteins in this pathway are associated with p16 status, we constructed a tissue microarray (TMA) with 46 archived tonsil squamous cell carcinoma specimens (24). The TMA was interrogated with antibodies directed against proteins in this pathway and against p16. The antibody panel included anti-eIF4E^{Ser209}, because phosphorylation of eIF4E appears to be essential for oncogenic activity (19, 25).

We demonstrated that downstream components of the PI3K pathway, such as phosphorylated Akt and S6, are expressed in the majority of the specimens (24), in agreement with the results of the Head and Neck Cancer Tissue Array initiative (26). Sixty-five percent of the tumors expressed p16, the marker for HPV-driven carcinogenesis (10-12). The salient new finding was that p16 expression was associated with expression of phosphorylated eIF4E ($p = 0.03$, Table 1) (24). Expression of p16 also correlated with expression of p21 ($p = 0.02$, Table 1) (24), in agreement with the immunohistochemistry study of Hafkamp (8). There was no association between expression of p16 and phosphorylated S6 or phosphorylated 4E-BP1. In agreement with multiple reports regarding HPV-status and tobacco history (2, 3), we found a significant correlation between history of tobacco abuse (>10 pack/years) and absence of p16 expression ($p = 0.01$) (24).

Table 1. Associations between anti-p16 and 8 other antibodies (24)

Antigen	Number p16 positive	Number p16 negative	P value*
p21			0.02
Pos (%)	25 (78)	7 (22)	
Neg (%)	5 (38)	8 (62)	
PTEN			0.02
Pos (%)	24 (77)	7 (23)	
Neg (%)	6 (40)	9 (60)	
Phospho eIF4E^{Ser209}			0.03
Pos (%)	26 (74)	9 (26)	
Neg (%)	4 (9)	7 (91)	
Phospho 4E-BP1^{Thr37/46}			1.0
Pos (%)	20 (67)	10 (33)	
Neg (%)	9 (64)	5 (36)	
Phospho AKT^{Ser473}			0.12
Pos (%)	21 (75)	7 (25)	
Neg (%)	9 (50)	9 (50)	
Phospho S6^{Ser240/244}			1.0
Pos (%)	19 (63)	11 (37)	
Neg (%)	10 (67)	5 (33)	
Phospho S6^{Ser235/236}			0.75
Pos (%)	13 (65)	7 (35)	
Neg (%)	17 (71)	7 (29)	
p53			1.0
Pos (%)	11 (65)	6 (35)	
Neg (%)	19 (68)	9 (32)	

*P values determined by Fisher's exact test

Note: For the following antibodies, tumor sample was missing from the TMA for one patient each: p21, p53, phosphorylated S6^{Ser240/244}. Tumor sample was missing from the TMA for two patients each for: phosphorylated 4E-BP1^{Thr37/46} and phosphorylated S6^{Ser235/236} (24).

The association between p16 and phosphorylated eIF4E expression has potential implications for clinical study. In the context of the central role of eIF4E in the translation of proteins encoded by capped mRNAs (27), the association between p16 and phosphorylated eIF4E may reflect interplay between virus and cellular translational apparatus. In cells infected with herpes simplex virus-1 or vaccinia virus, phosphorylation of eIF4E by Mnk-1 is critical for viral protein synthesis and replication (28, 29). It is not known if similar mechanism occurs in HPV-positive HNSCC, but HPV is associated with increased cap-dependent translation in differentiating cervical cancer cell lines (30), and eIF4E staining is increased in cervical neoplasia (31).

In summary, several observations indicate that eIF4E is an attractive research target in HPV/p16 positive tonsillar squamous cell carcinoma: (1) eIF4E expression has prognostic significance in HNSCC (2) eIF4E knockdown in HNSCC cell lines is associated with reduced tumorigenicity (3) phosphorylated eIF4E is associated with p16 status in a tonsil squamous cell carcinoma tissue microarray (4) eIF4E is critical for viral protein synthesis in other systems.

3.4 Ribavirin is a broad-spectrum antiviral agent that inhibits eIF4E

In 1972, the guanosine ribonucleotide analogue ribavirin (Virazole®; 1-β-D-ribofuranosyl-1,2,4-triazole-3-carboxamide) was reported to have broad spectrum activity against both RNA and DNA viruses. The combination of ribavirin + peginterferon (PEG-IFN) α-2b is an effective treatment for chronic hepatitis C. The most common adverse events associated with ribavirin are mild anemia, cough, and rash. For patients treated with prolonged ribavirin, anemia usually is mild and hemoglobin remains in the normal range (32, 33). Risk factors for moderate to severe anemia with ribavirin are advanced age, low body weight, hepatic or renal insufficiency, and baseline marrow dysfunction (34-36). In the current study, eligibility criteria exclude patients with factors that might put them at increased risk of anemia with ribavirin.

The pivotal trial (n = 1530 subjects) establishing PEG-IFN α-2b + ribavirin efficacy against chronic hepatitis C showed that treatment for 48 weeks with PEG-IFN α-2b (1.5 µg/kg/week) and a flat dose of ribavirin (800 mg/day) was statistically superior to IFN α-2b or low-dose (0.5 µg/kg/week) of PEG-IFN α-2b and weight-based dose of ribavirin (1000 – 1200 mg/day) (37). A subsequent randomized clinical trial (n = 5027 subjects) demonstrated that a weight-based ribavirin (800 – 1400 mg/day) + PEG-INF α-2b was more effective than flat-dose ribavirin (800 mg/day) + PEG-IFN α-2b (38). However, the improvement in sustained virologic response was modest (44.2% for weight-based dosing versus 40.5% for flat dosing), and appeared to be restricted to patients with HCV genotype 1. Additionally, mean hemoglobin levels decreased to a lesser extent in the flat-dose group than in the weight based-group (38). In the current protocol, ribavirin will be given at flat dose of 800 mg/day to optimize patient safety.

Ribavirin has been reported to have clinical activity against laryngeal papillomatosis (LP) in a small non-randomized pilot study (39). LP, a rare condition with an incidence of approximately 7.1 per million in the U.S., is an HPV-related disease in which the upper airway becomes progressively occluded with mucosal papillomas. Repeated laser surgery for removal of lesions has been commonly applied as a management strategy. In the pilot study, patients (3 adults, 1 child) received pre-operative ribavirin (23 mg/kg daily) on the day of laser surgery, and continued oral ribavirin at the same daily dose for an additional 6 months (only 3 months for the child). The viral strain was HPV-6 in the papillomas of three patients, and was HPV-11 in one patient.

Treatment was generally well tolerated, with only one patient requiring a 25% dose reduction for anemia, which resolved with continued treatment at the reduced dose. Ribavirin treatment was associated a decrease in observable disease on follow up examinations, as determined by a previously described mapping score. Ribavirin treatment was associated with an increase in the time interval between successive required surgeries by a factor of at least 2 in all patients (39). No pharmacodynamic correlates were done in this study. The efficacy of ribavirin against laryngeal papillomatosis was confirmed in a subsequent case report (40), and ribavirin is considered to be one treatment option for this uncommon entity (41).

The mechanism of ribavirin's antiviral activity is not conclusively established, and at least five potential mechanisms have been proposed (42). For example, ribavirin is a potent competitive inhibitor of cellular inosine monophosphate dehydrogenase (IMPDH), thereby depleting GTP pools that are necessary for viral nucleic acid synthesis. Ribavirin also inhibits viral 7-methylguanosine (m⁷G) RNA cap synthesis in vaccinia virus (43, 44). These two mechanisms may be complementary: by reducing levels of competing GTP, ribavirin

MEMORIAL SLOAN-KETTERING CANCER CENTER IRB PROTOCOL

IRB#: 10-218 A(8)

may be more effective as a capping inhibitor (42). The precise mechanism of ribavirin may be influenced by the particular virus and cell type, but the capping inhibition mechanism may be potentially relevant for those viruses that produce capped transcripts, such as HPV-16.

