6.0 CRITERIA FOR SUBJECT ELIGIBILITY

6.1 Subject Inclusion Criteria

1. Prior diagnostic surgical or core needle biopsy, with confirmation of tonsil and/or base of tongue squamous cell carcinoma that is positive for expression of p16 and phosphorylated eIF4E, as determined by the Department of Pathology at MSKCC. The biopsy may be either of the tonsil, base of tongue, and/or an involved neck node. 2 unstained slides and/or tissue block must be available from the initial diagnostic biopsy

Positive expression p16 and phosphorylated eIF4E is defined as $\geq 30\%$ of tumor cells with cytological and/or nuclear staining

2. Age ≥ 18 and ≤ 65 years of age
3. Karnofsky Performance Status ≥ 80
- 4.

Adequate organ function, as follows:

Adequate bone marrow reserve: absolute neutrophil count (ANC) $\geq 1.5 \times 10^9/L$, platelets $\geq 160 \times 10^9/L$, hemoglobin $\geq 12 \text{ g/dL}$

Hepatic: total bilirubin within $1.5 \times$ upper limit of normal (ULN) ; alkaline phosphatase (AP), aspartate transaminase (AST) and alanine transaminase (ALT) $\leq 2.5 \times$ ULN

(Patients with Gilbert's syndrome as the cause of hyperbilirubinemia may be eligible if total bilirubin $\leq 2.5 \times$ UNL)

Renal: Serum creatinine $\leq 1.3 \text{ mg/dL}$. Patients with serum creatinine $> 1.3 \text{ mg/dL}$ may be eligible if creatinine clearance (CrCl) $\geq 55 \text{ mL/min}$ based on the standard Cockroft and Gault formula.

5. Patients of childbearing potential must have a negative serum pregnancy test within 14 days of treatment. Patients must agree to use a reliable method of birth control during and for 6 months following the last dose of study drug.
6. Ability to swallow oral medication.
7. Non-surgical patients: If primary radiation +/- chemotherapy (concurrent or sequential) is planned, patients must agree to undergo research biopsy after completion of ribavirin treatment.

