6.2 Subject Exclusion Criteria

1. Prior chemotherapy or radiation for tonsillar or base of tongue squamous cell cancer
2. More than 10 pack-years of tobacco use
3. History of hemolytic anemia or thalassemia
4. Active infection or serious underlying medical condition that would impair the patient's ability to receive protocol treatment.
5. Current therapeutic anticoagulation with Coumadin (warfarin)
6. Current or prior treatment with ribavirin
7. Known active Hepatitis B or C
8. Any prior documented history of transient ischemic attack (TIA) or cerebrovascular accident (CVA)
9. New York Heart Association (NYHA) Grade II or greater congestive heart failure
10. Clinically significant peripheral vascular disease
11. History of unstable angina or myocardial infarction (MI) within the last 3 years

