10.1 EVALUATION DURING TREATMENT/INTERVENTION

10.2 Description of Evaluations

Patients will be provided with a pill diary at the start of treatment (Appendix A), and will be required to bring a updated pill diary to each clinic visit. If patients miss any doses of ribavirin, this will not be considered a protocol violation but the investigator retains the discretion to remove patients from study for non-compliance.

Every attempt will be made for patients to have clinic visits and laboratory tests on the indicated dates. However, dates may need to be altered for medical or personal or logistical reasons. Clinic visits and laboratory studies may occur 3 days before or 3 days after the scheduled date, if need be. Additional clinical visits and laboratory studies may be scheduled if clinically necessary, per investigator discretion.

- On Day 1, routine laboratory studies are obtained: complete blood cell count and comprehensive metabolic panel. Patients undergo history and physical.
- Days 1 – 14, approximately: ribavirin 800 mg/day in divided doses, 400 mg q AM and 400 mg q PM. Typically, this will be administered as two 200 mg tablets qAM, and two 200 mg tablets qPM. Use of one 400 mg tablet (instead of two 200 mg tablets) is also allowed, at the discretion of the investigator.
- On Day 8, Routine laboratory studies are obtained: complete blood cell count and comprehensive metabolic panel. Patients undergo history and physical.
- Day 15 (approximately): Surgical plan is resection or research biopsy of the tonsil and/or base of tongue squamous cell carcinoma, possibly with neck dissection at the discretion of the surgeon. Patients will be considered done with treatment at time of surgery or research biopsy. As such, the surgical or biopsy procedure is considered off-protocol, and the surgery or research biopsy will be performed at the discretion of the investigator. The protocol provides no guidance nor places any restrictions regarding surgical management.

While every attempt will be made to schedule surgery or research biopsy on Day 15, the exact timing of surgery or research biopsy will be at the discretion of the surgeon. No ribavirin will be given after surgery or research biopsy.

- Post-operative (or post research biopsy) management will be per standard of care, off protocol.

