11.2 Hematologic Toxicity

The most common toxicity requiring dose reduction for ribavirin is anemia.

For any patient who experiences a fall in hemoglobin of > 2 g/dL (from Day 1 value), ribavirin dose will be decreased to 600 mg/day (200 mg qAM, 400 mg qPM). Any patients who develop a hemoglobin level of < 10 g/dL will be removed from study.

Any patient who develops a platelet count of < 100 K/mcL will be removed from study. Any patient who develops an absolute neutrophil count of < 1.0 K/mcL will be removed from study. Dose delays and dose reductions are not required for uncomplicated leukopenia or uncomplicated lymphopenia.

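### Section 6.1 tests creatinine clearance only above creatinine 1.3 mg/dL and sets no weight criterion, so it falls short of the anemia safeguard claimed in 3.4 (low priority, cheap to fix)

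*Combined protocol and SAP*

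**What the plan says.** Section 3.4 states: "Risk factors for moderate to severe anemia with ribavirin are advanced age, low body weight, hepatic or renal insufficiency, and baseline marrow dysfunction". Its next sentence says that, in this study, "eligibility criteria exclude patients with factors that might put them at increased risk of anemia with ribavirin".

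The criteria that bear on those factors are these:

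- **Age:** 18 to 65 years (6.1).
- **Marrow:** neutrophils at least 1.5 and platelets at least 160 (both ×10⁹/L), hemoglobin at least 12 g/dL (6.1). Section 6.2 also excludes a history of hemolytic anemia or thalassemia.
- **Hepatic:** limits on bilirubin, alkaline phosphatase, AST and ALT (6.1).
- **Renal:** creatinine of 1.3 mg/dL or less qualifies by itself. Above 1.3, a patient can still qualify with a clearance of at least 55 mL/min, "based on the standard Cockroft and Gault formula" (6.1).
- **Body weight:** no criterion in 6.1 or 6.2.

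**The concern.** The sentence in 3.4 works as a safety assurance, and it carries no qualification. Three of the named factors (age, hepatic function, marrow) have a matching limit. Low body weight has none. Renal function has a limit that changes form at creatinine 1.3 mg/dL.

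Serum creatinine alone takes no account of age, sex or weight, whereas the Cockcroft-Gault formula uses all three. A patient who is older, lighter or female can meet the creatinine limit with a lower estimated clearance than someone refused by the clearance test. Section 5.2 associates these same three characteristics with lower apparent ribavirin clearance.

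What is at stake is patient safety at entry, not inference. Section 11.2 says: "The most common toxicity requiring dose reduction for ribavirin is anemia". Section 3.6 notes that mild anemia often appears within two weeks, which is the length of treatment here.

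**Working it through.** The plan prints no figure on this point to reproduce. The check is whether the two renal routes in 6.1 order patients consistently.

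**Inputs.** From 6.1: maximum age 65, creatinine cut-off 1.3 mg/dL, clearance cut-off 55 mL/min, and the named formula. The protocol does not print the formula; its standard form is

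CrCl = (140 − age) × weight in kg / (72 × creatinine), multiplied by 0.85 for women.

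The documents give no weights or creatinine values for the expected patients. Those below are assumptions, chosen to show the range.

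**Patients under the current text.**

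| Patient | Calculation | CrCl (mL/min) | Current 6.1 |
|---|---|---|---|
| Woman 55, 60 kg, 1.2 | 85 × 60 × 0.85 / 86.4 | 50.2 | admitted |
| Woman 60, 65 kg, 1.2 | 80 × 65 × 0.85 / 86.4 | 51.2 | admitted |
| Man 60, 60 kg, 1.3 | 80 × 60 / 93.6 | 51.3 | admitted |
| Woman 65, 60 kg, 1.1 | 75 × 60 × 0.85 / 79.2 | 48.3 | admitted |
| Woman 65, 50 kg, 1.3 (extreme) | 75 × 50 × 0.85 / 93.6 | 34.1 | admitted |
| Man 65, 67.9 kg, 1.31 | 75 × 67.9 / 94.32 | 54.0 | refused |

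The ordering is inverted: every admitted patient in the table has a lower estimated clearance than the one refused.

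**Who can be affected.** Setting CrCl = 55 at the least favorable admitted values (age 65, creatinine 1.3) gives the highest weight at which a patient can fall short:

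- Men: 55 × 72 × 1.3 / 75 = 68.6 kg.
- Women: 68.64 / 0.85 = 80.8 kg.

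Heavier patients always reach 55 under the present age and creatinine limits. At younger ages or lower creatinine the weight limits fall. At age 55 and creatinine 1.3, for example, they are 60.6 kg for men and 71.3 kg for women.

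For a 60 kg patient, clearance drops below 55 once creatinine exceeds (140 − age) × 60 / (72 × 55), times 0.85 for women:

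| Age | Men | Women |
|---|---|---|
| 55 | 1.29 | 1.09 |
| 60 | 1.21 | 1.03 |
| 65 | 1.14 | 0.97 |

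The inversion is therefore not confined to the extreme corner of the criteria, but it does need a fairly light patient with creatinine towards the upper part of the permitted range.

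**The case against.** **The 55 mL/min figure is not a universal floor.** A reader might infer that the protocol breaches its own renal limit. It does not. The figure is written as a second route for patients above 1.3 mg/dL, and renal insufficiency is not defined. Nothing in the documents shows that creatinine of 1.3 or less fails to exclude renal impairment that matters for anemia. This stands. What remains is that two routes to the same criterion rank patients inconsistently.

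**Harm is not shown.** A reader might infer that the admitted patients face a demonstrated excess of anemia. The documents do not quantify risk at clearances of 48 to 54 mL/min. Section 3.4 says anemia is usually mild even with prolonged treatment, and it chose the flat 800 mg/day dose for safety. It reports good tolerance at 23 mg/kg daily in 4 patients (one 25% reduction for anemia) and from 1000 mg/day in 13 (no reduction for toxicity). At 50 kg the present dose is 800/50 = 16 mg/kg. Those groups are small and their renal function is not reported, but the objection stands as a limit on the weight of the point.

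**Other safeguards exist.** Entry hemoglobin is at least 12 g/dL. A fall of more than 2 g/dL lowers the dose to 600 mg/day, and a value under 10 g/dL ends participation (11.2). Section 11.3 allows discretionary reduction. Section 6.2 excludes "Active infection or serious underlying medical condition that would impair" ability to receive treatment, although an estimated clearance of 48 with creatinine 1.1 would not clearly qualify. These safeguards limit harm but do not correct the entry test.

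**Monitoring.** A reader might infer from the single on-treatment count scheduled for Day 8, with its three-day window (10.2), that late anemia would go unseen. Section 4.3 requires laboratory studies weekly or more often, and 10.2 permits extra tests. An eligibility change would add no blood count in any case, so this forms no part of the point.

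**Sex, age and weight matter little.** Section 5.2 says they explain under 30% of the variability in ribavirin clearance. That is a reason for modesty, but 3.4 lists renal insufficiency as a risk factor separately.

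**The sentence in 3.4 may be loose rather than wrong.** It can be read as saying that some such factors are excluded, which is true. It is also background text that governs no enrolment decision, so rewording it would not justify a change by itself.

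**Conclusion.** The concern holds as a low-priority safety improvement. The renal criterion admits some patients with lower estimated clearance than others it refuses, and low body weight, a named risk factor, is not addressed. The assurance in 3.4 is therefore broader than the criteria behind it. The remaining factors are covered.

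The arithmetic rests on the standard Cockcroft-Gault formula and on illustrative weights and creatinine values. Frequency cannot be estimated from the documents; among 7 evaluable patients, none or one is a reasonable judgment. The primary endpoint, the 4-of-7 decision rule and its operating characteristics do not change.

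**What to change.** In 6.1, replace the renal item with: *Renal: Cockcroft-Gault creatinine clearance ≥55 mL/min for all patients, calculated from baseline creatinine, age and weight.* This uses the formula and figure already in the protocol and removes the inversion.

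As a consequential edit in 3.4: *Eligibility criteria limit age, hepatic, renal and marrow risk factors for anemia; low body weight is not itself an exclusion.* No separate weight threshold is proposed. Because weight enters the formula, the renal rule will screen out some light patients indirectly: at 50 kg and age 65, creatinine could be no higher than about 0.95 mg/dL for a man or 0.80 for a woman.

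The cost is amendment wording and one calculation per patient. Creatinine is already in the baseline panel (8.1); weight is assumed to be recorded at the baseline examination. The rule admits nobody new and will occasionally refuse someone now eligible, more often a woman. A 65-year-old, 60 kg woman with creatinine 1.0 has a clearance of 75 × 60 × 0.85 / 72 = 53 mL/min and would no longer qualify. At the planned 1 to 2 patients per month (14.0), each patient lost adds 0.5 to 1 month, about 2 to 4 weeks, to an accrual expected to take 4 to 7 months.
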